3.1 Statistical Analysis

The data analyst will be blinded to the cup assignment. We will use generalized estimating equations for a crossover design to assess intake, spillage, and feeding duration and a sign test to assess the caregiver’s preference. Covariates may include factors such as amount of prior feeding, type of nutrition, number of prior cup feeds with assigned cup, and number of cup feeds between measured feedings. Most covariates typically accounted for (maternal age, other demographics) will not be included because the comparison is the same caregiver/infant pair.

We will conduct exploratory analyses stratifying on age (0-14 days and 15-28 days) and gestational age (<34 weeks and 34-36 weeks) to evaluate potential effect modification by these factors. These are exploratory since this study was not powered to detect effect modification. For each cup separately, we will compare estimates for those assigned the cup first to estimates for those assigned the cup second to evaluate for design effects. If design effects are observed we will analyze our data comparing those first assigned the Nifty cup to those first assigned to the medicine cup, dropping the data from the second cup and removing the cross over design from our study. We will use Stata 13.0 for all statistical analysis. Consistent with our power calculations, a two-sided p-value of 0.05 will be used.

A strength of our statistical approach is that participants with outcome data for at least one feeding assessment are able to be included in our GEE analyses even if other time points are missing. We will evaluate the potential effect of other missing data on our associations using multiple imputation methods.¹²

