4.2 Study Eligibility: Inclusion and Exclusion Criteria Inclusion

In order to be eligible to participate in this study, the caregiver-infant pair must meet all of the following. The information in [brackets] specifies where this information will typically be ascertained. A caregiver is the person primarily responsible for feeding the infant. This is typically the mother. In cases where the mother is unwell or deceased, we may enroll a caregiver who is a biological family member designated as the person primarily responsible for feeding the infant. Relations who meet this criterion include a biological grandmother or aunt of the infant. The admitting doctors will do the scoring using the physical characteristics of the modified Dubowitz assessment tool (see final page of this document). The admitting doctors will be House Officers supervised by Paediatric Residents and will be qualified (BSc Human Biology, MB ChB – which is analogous to MD) and members of the Ghana College or the West Africa College of Physicians.

Inclusion

- Infant
 - Infant was born preterm (<37 weeks gestational age) at time of birth [chart]
 - Infant's corrected gestational age is <37 weeks per the modified Dubowitz score on date of enrollment [chart].
 - Infant diagnosed with feeding difficulties [provider]
 - Infant is a patient in the mother-baby unit at KATH [chart/location]
 - Infant is clinically indicated to start cup feeding (including an infant who has a nasogastric tube and is cup feeding or indicated to start cup feeding) [provider]
 - Infant has an anticipated hospital stay that is at least 48 hours [provider]
- Caregiver:
 - Caregiver must be at least 18 years of age [caregiver]
 - Caregiver must be one of the following biologic family members of the infant [caregiver]:
 - Mother
 - Grandmother
 - Aunt
 - Caregiver must self-identify as the primary feeder of the infant [caregiver]

- Prior experience feeding the potential infant participant with nipple feeding (e.g. breast feeding, bottle feeding, or nasogastric [NG] tube) is okay but is not required [caregiver].
- Caregiver verifies willingness to comply with all study procedures [caregiver]

Exclusion

- Infants with a congenital anomaly except for minor anomalies (e.g. an extra digit or ear tag is okay) [provider]

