A copy or duplicate of the signed informed consent document will be given to the caregiver/parent for their records. A copy is a photocopy of the original signature consent. A duplicate is a second consent form with all originally signatures. A duplicate will be used when a copier is not readily available. The rights and welfare of the caregiver/parent will be protected by emphasizing to them that the quality of the infant's clinical care will not be adversely affected if they decline to participate in this study. The caregiver/parent may withdraw consent at any time throughout the course of the study.

Informed consent will take place *at least* 24 hours after the birth of the child to allow for birth related care to take place, including the identification of the infant as preterm. The RA will obtain permission from the health care provider to approach the caregiver/parent about the study as part of the screening process. Those participants unable to write their name have the option of providing a fingerprint and having the RA write in their name. Fingerprint consent will be observed by a witness who will also sign the consent form. The consent witness will be an impartial witness and not a family member. We have identified several types of individuals that could serve as impartial consent witnesses for mothers who are not literate. These include the following: (1) hospital administrators, (2) technology support individuals, (3) nurses on other surgical or medical wards (those in the mother-baby unit will not serve as consent witnesses), or (4) records officers.

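### Effect modification is to be evaluated by stratified analyses with no between-stratum comparison specified, and the age strata do not cover every eligible infant

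*Combined protocol and SAP*

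**What the plan says.** Section 3.1 names the main model: "We will use generalized estimating equations for a crossover design to assess intake, spillage, and feeding duration". As exploratory work it then plans "stratifying on age (0-14 days and 15-28 days) and gestational age (<34 weeks and 34-36 weeks) to evaluate potential effect modification by these factors" and qualifies this: "These are exploratory since this study was not powered to detect effect modification". It sets a two-sided 0.05 level for the analysis. Neither section 3.1 nor any other section names an interaction term, a heterogeneity test or another way of comparing the strata.

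Two inclusion criteria in section 4.2 concern gestational age. One is "Infant was born preterm (<37 weeks gestational age) at time of birth". The other is that the infant's "corrected gestational age is <37 weeks per the modified Dubowitz score on date of enrollment". Neither these nor the exclusion criteria cap age in days. At the lower end, section 7.0 allows consent from "24 hours after the birth of the child to allow for birth related care to take place". The 28 days in section 4.1 describes survival among infants counted in 2013 to size the recruitment pool; it is not an enrolment limit.

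**The concern.** Two separate stratum results do not estimate how far the cup effect differs between strata. In small strata, one result can reach significance and the other miss it when the cup works equally well in both. A reader could then conclude that the cup helps only some infants. An interaction estimate with its interval addresses the question directly and shows how little the data can say.

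The second issue is coverage. The upper age stratum has a ceiling that eligibility does not have. An eligible infant older than 28 days would be left out of the age analysis as defined. That omission is not random with respect to gestational age at birth, because only infants born early enough can reach that age while still under 37 weeks corrected.

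**Working it through.** **Inputs from section 2.3.** 150 pairs (up to 200), a 5% difference, SD 11 (unit not stated), correlation 0.02 to 0.5, two-sided paired t-test, alpha 0.05.

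**Assumptions.** The 5% is read as 5 units on the scale of the SD. There is one measurement per cup. The stratum splits are mine, since the documents give no expected distribution by age or gestational age.

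**1. The plan's own power figures.** SD of the within-pair difference = 11 × √(2(1 − ρ)), which is 15.4 at ρ = 0.02 and 11.0 at ρ = 0.5. With 150 pairs, the paired t-test (noncentral t) has 97.7% and over 99.9% power for 5 units. The stated 90% is therefore conservative on this reading. The stated 80% under carryover is reproduced: 75 against 75 on the first cup alone gives 79.0%. No figure is given for the stratified analyses, and nothing below depends on the 90%.

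**2. Reading strata by separate p-values.** Let the true effect be 5 units in both strata. With stratum powers p₁ and p₂, and different infants in each, P(exactly one significant) = p₁(1 − p₂) + p₂(1 − p₁).

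| Split (pairs) | ρ = 0.02: p₁, p₂ | Exactly one | ρ = 0.5: p₁, p₂ | Exactly one |
|---|---|---|---|---|
| 75/75 | 0.793, 0.793 | 33% | 0.973, 0.973 | 5% |
| 100/50 | 0.895, 0.614 | 41% | 0.995, 0.883 | 12% |
| 120/30 | 0.942, 0.405 | 58% | 0.999, 0.672 | 33% |

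For example, 120/30 at ρ = 0.02 gives 0.942 × 0.595 + 0.405 × 0.058 = 0.584.

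At 200 pairs the figures fall to 19% and 1% (100/100), and to 48% and 20% (160/40).

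Section 5.1 provides two measured feeds per cup. If SD 11 applies to a single feed and the two feeds with the same cup correlate at 0.5 (an assumption), the variance of a cup mean is 11² × (1 + 0.5)/2. The ρ = 0.02 column at 150 pairs then becomes about 19%, 28% and 49%.

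**3. What an interaction test gives.** With equal effects it rejects in about 5% of trials by construction. Its standard error is SD of difference × √(1/n₁ + 1/n₂). For 75/75 this is 15.4 × √(2/75) = 2.51 at ρ = 0.02 and 11.0 × √(2/75) = 1.80 at ρ = 0.5. Power for a true 5-unit difference between strata, Φ(5/SE − 1.96), is 51% and 80%. For 120/30 it is 36% and 61%.

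**4. Age coverage.** An infant stays under 37 weeks corrected until the day before 37 weeks 0 days, so maximum eligible age in days = 259 − (gestational age at birth in days) − 1.

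| Born at | Days at birth | Maximum eligible age |
|---|---|---|
| 32w6d | 230 | 28 days |
| 32w5d | 229 | 29 days |
| 32w0d | 224 | 34 days |
| 30w0d | 210 | 48 days |
| 28w0d | 196 | 62 days |

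The gap thus opens for births at 32 weeks 5 days or earlier. These ages are upper bounds from one criterion, not expected ages at enrolment.

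**The case against.** The strongest reply is that the plan states no decision rule. It stratifies "to evaluate potential effect modification by these factors", does not say it will contrast a significant stratum with a non-significant one, and does not rule out an interaction term. It also states openly that the study is unpowered for this. That stands, and it limits the claim. A reader might infer that the investigators intend to claim benefit in one stratum only; the documents do not support that. What remains is that no between-stratum comparison is specified, and calling the analysis exploratory does not supply one.

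It is also fair that the percentages use assumed splits, one measurement per cup and the smaller sample size. They fall at 200 pairs or with both feeds.

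On age, the number of infants over 28 days could be zero. Eligibility also requires inpatient status in the mother-baby unit, diagnosed feeding difficulties and an indication for cup feeding, and the background describes the target as newborns. Two stronger readings are tempting. One is that the most premature infants are lost: not so, since an infant born at 28 weeks and enrolled on day 10 or 20 falls within a stratum. The other is that effect modification is most plausible in the omitted infants; nothing in the documents supports this. If gestational age in section 3.1 means age at birth (the text does not say), every infant over 28 days is still in the under-34-week stratum.

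Finally, the 28-day ceiling may reflect an intended age limit missing from section 4.2. That is possible, and it would still leave the two sections to be reconciled.

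**Conclusion.** The point holds as a minor one, in two parts. First, effect modification is to be evaluated by stratifying alone, with no comparison between strata specified. Were the strata read by separate p-values, a spurious contrast could arise in roughly 5% to 58% of trials of 150 pairs, depending on correlation and split. That range rests on 5% meaning 5 units, SD 11, one measurement per cup, my assumed splits and a reading rule the plan does not state. It is an illustration, not a prediction.

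Second, the age strata leave out any eligible infant older than 28 days. This follows from sections 3.1 and 4.2 without assumptions, but how many infants it concerns is unknown. A reader might infer that they drop out of the trial's main result. They do not: they are missed only by the exploratory age split. The hypotheses in section 2.2, the sample size and the main cup comparison are unaffected.

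**What to change.** In the planned GEE, add cup-by-age and cup-by-gestational-age interaction terms. Report each interaction estimate with its confidence interval beside the stratum estimates, and keep the analysis exploratory.

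Define the upper age stratum as 15 days or older, or use age as a continuous variable, so that every enrolled infant is included. If a 28-day age limit was intended, sections 3.1 and 4.2 must be reconciled instead.

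The cost is two model terms and one changed label, with no new data, visits or participants. The downside is modest power: about 51% to 80% for a 5-unit difference between equal strata at 150 pairs, and less if the strata are unequal. A non-significant interaction therefore should not be read as evidence that the effect is the same in all infants; the confidence interval should carry the message.

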2.3 Statistical Justification

Power for this study was determined by our primary hypotheses for the study H_A 1 related to amount of spillage and H_A 2 related to intake of milk. With 150 (up to 200) pairs, we estimate we will be able to detect at least a 5% difference in spillage or intake with 90% power and an alpha of 0.05 if no design effects are present. Carryover effects occur when a participant learns from cup feeding with the first cup which then affects the outcomes when feeding with the second cup. We will be able to statistically evaluate if carryover effects are present. If carryover effects are observed, we will have 80% power to detect an average 5% difference in spillage or intake.

These estimates are based on studies report differences in intake and spillage.⁸⁻¹⁰ We used the ‘power’ command in Stata 13.0 to estimate power using a two-sided paired t-test. We selected a conservative difference based on other studies, which showed differences between 6.3 and 7.8ml.⁸⁻¹⁰ We used a published estimate of a cup feeding standard deviation of 11¹⁰ and conservative correlations ranging from 0.02 to 0.5. This power calculation is also applicable to a 5% difference caregiver satisfaction between the two cups.

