5.1.3 Visit 3. Cup 1 Feed 2 (Day 1, >2 hours after V2)

The RA will measure a second feeding at V3. There may or may not be feedings between V2 and V3. During Visit 3, the RA will:

- Conduct the Feeding Assessment
- Remove Cup 1 so it is not inadvertently or preferentially used over Cup 2
- Provide the caregiver with Cup 2 and the instructions for use.

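### Section 3.1 abandons the crossover on a within-cup order check that cannot tell unequal carryover from a harmless period effect or equal learning

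*Combined protocol and SAP*

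**What the plan says.** Section 3.1 analyses intake, spillage and duration by GEE for a crossover and then adds a check: "For each cup separately, we will compare estimates for those assigned the cup first to estimates for those assigned the cup second". If design effects appear, the response is "dropping the data from the second cup and removing the cross over design from our study". The term design effects is not defined. The only significance level in the section is general: "Consistent with our power calculations, a two-sided p-value of 0.05 will be used". The section does not say whether one cup or both must differ, or which outcome decides.

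No period term is named. One possible covariate, "number of prior cup feeds with assigned cup", is optional and counts feeds with the current cup only.

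Section 2.3 treats as carryover any learning with the first cup that goes on to influence results with the second; it need not differ by order. The section plans for both outcomes of the check: a 5% difference "with 90% power and an alpha of 0.05 if no design effects are present", and otherwise "If carryover effects are observed, we will have 80% power to detect an average 5% difference in spillage or intake".

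Under Sections 5.1.2 to 5.1.5, Cup 1 feeds are measured on Day 1 and Cup 2 feeds on Day 2. Cup 2 is handed over at the visit where staff "Remove Cup 1 so it is not inadvertently or preferentially used over Cup 2", so there is no washout.

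**The concern.** The check decides which of two analyses produces the spillage result, so it should respond to what would invalidate the crossover and to little else. It does not. Infants are starting cup feeding and caregivers are practising, so some change from Day 1 to Day 2 is plausible whichever cup came first. Such a change shifts both within-cup comparisons and, on Section 2.3's definition, can count as carryover, although it does no harm to a period-adjusted contrast.

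Two things are at stake. Precision can be lost when the crossover estimate would have been unbiased. The error rate also rises, because the same data choose the analysis and supply the test.

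**Working it through.** **Inputs.** From Section 2.3: 150 pairs (up to 200), SD 11, correlation ρ from 0.02 to 0.5, difference 5, two-sided 0.05. Assumed: 1:1 sequences (75 each at N=150), the check run at p<0.05, and the period and carryover sizes, none of which the documents give. Section 2.3 sets SD 11 beside differences in ml, while Section 5.2.2 reports spillage as a percent. Sizes are therefore best read in SD units: 5/11 = 0.45 SD and 3/11 = 0.27 SD.

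**The plan's own power figures.**
- Fallback: SE = 11·√(2/75) = 1.796, and 5/1.796 = 2.78. Power is 79.0% by noncentral t, so the stated 80% reproduces.
- Crossover, 150 pairs: SE = 11·√(2(1−ρ))/√150 = 1.257 at ρ=0.02 and 0.898 at ρ=0.5. Power is 97.7% and over 99.9%. The stated 90% is therefore understated on these inputs; nothing below depends on it.

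**What each comparison estimates.** Let τ be the cup effect (Nifty minus generic), π the period effect, and λN and λG the carryover into period 2 after Nifty first and generic first.

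| Sequence | Period 1 | Period 2 |
|---|---|---|
| Nifty, then generic | μ + τ | μ + π + λN |
| Generic, then Nifty | μ | μ + τ + π + λG |

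- Check within Nifty, second minus first: π + λG.
- Check within generic, second minus first: π + λN.
- Period-adjusted crossover contrast: ½[(τ − π − λN) − (−τ − π − λG)] = τ + (λG − λN)/2.
- First-period contrast: τ.
- Sequence contrast (difference in within-pair sums): λN − λG.

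A common π, or λN = λG, moves both checks and drops out of the crossover contrast. Only λN ≠ λG biases it, by half the difference.

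**Cost of switching.** Variance is 2σ²/75 for the first-period contrast and σ²(1−ρ)/75 for the crossover. The ratio is 2/(1−ρ), which is 2.04 at ρ=0.02 and 4.0 at ρ=0.5.

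**How often the rule fires.** These are simulated trials with bivariate normal cup means and t-tests in place of the GEE. The final test is the first-period test if the rule fires and the period-adjusted crossover otherwise. Ranges span ρ = 0.02 to 0.5. *Either* and *both* are the two readings of which cups must differ.

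| Setting | Fires: either | Fires: both | Power: either | Power: both | Crossover power |
|---|---|---|---|---|---|
| N=150, difference 5, period 3 | 62–69% | 7–14% | 83–85% | 96–99% | 97.7% to >99.9% |
| N=200, difference 5, period 3 | 74–81% | 15–23% | 90–91% | 98–99.7% | ≥99.5% |

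At N=150, equal carryover of 3 in both sequences gives the same *either* figures as a period effect of 3. The sequence contrast, tested at 0.05, fires in 5.0% of the N=150 period-3 trials. Smaller period effects at N=150, read as *either*: size 1 fires in 16–17% with power 93–94%; size 2 fires in 36–39% with power 88–89%.

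**Type I error, no cup effect and no design effect, N=150.** *Either* 6.3–7.6%; *both* 5.1–5.7%.

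**The case against.** **The fallback is sound and planned.** First-period data are unbiased for the cup effect, and Section 2.3 foresees 80% power. This stands. A reader might infer that the trial would miss its power target; the documents do not support that. Every power in the period-effect settings above exceeds 80%, and a period effect of 1 leaves 93–94%, above the planned 90%.

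**The large firing rates depend on the reading.** This also stands. The 62–69% needs the *either* reading, a test at 0.05 and an assumed period effect. Section 3.1 speaks only of comparing estimates, and its 0.05 sentence is general. The algebra needs none of these choices.

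**A crossover GEE may already contain a period term.** Possibly. Not naming one does not show that it is left out, and the point does not rest on its absence. With 1:1 sequences and complete data the simple contrast is balanced over period anyway.

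**The analyst is blinded** ("The data analyst will be blinded to the cup assignment"). That limits favouring a cup; it does not change how often the rule fires.

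**The rule protects against real carryover.** This is the strongest objection. Without washout, unequal carryover is credible. With carryover of 5 in one sequence only and no cup effect, the crossover rejects in 51–79% of trials at N=150 and 63–89% at N=200. The current rule read as *either* rejects in 14–19% and about 10–12%. Read as *both* it protects little: 49–77% and 61–87%. With a true difference of 5 and opposing carryover of 5 at N=150, crossover power is 51–79%, against 78–86% for the rule read as *either*. The protection is real on one reading, but it comes from a check that fires just as readily on harmless shifts.

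**Conclusion.** The point holds as a flaw in the decision rule and should be fixed. The within-cup check estimates period effect plus carryover and cannot isolate the unequal carryover that would justify leaving the crossover. The harm is lost precision (2 to 4 times the variance whenever the rule fires needlessly) and a type I error mildly above 5%. The fallback is neither biased nor unplanned.

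The algebra assumes shifts that are additive on the analysis scale. The variance ratio and simulated figures also rest on Section 2.3's SD and correlations taken on a common scale and on 1:1 sequences. The simulated figures further assume the check at 0.05 and illustrative effect sizes.

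A reader might extend the point to the satisfaction rating taken at Visit 5 after both cups. That is a separate gap: the instruction to drop data follows the GEE outcomes, and Section 3.1 names no method for rated satisfaction under any scenario. Preference has its own sign test.

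**What to change.** In Section 3.1, delete the within-cup comparison as a trigger and the sentence that drops second-cup data. Insert:

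> The primary analysis of spillage, intake and duration is the crossover GEE with terms for cup and period, using all feeds from all pairs; it does not depend on any design-effect test. The first-period-only comparison of the cups with its 95% CI will always be reported as a prespecified sensitivity analysis, with the sequence (differential-carryover) contrast and its 95% CI. A non-significant contrast will not be read as absence of carryover.

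Two alternatives should be avoided:
- **The sequence contrast as a new trigger.** Type I error with no design effect would still be 6.4–7.4%.
- **A compulsory carryover label on any positive crossover result without first-period significance.** With a true difference of 5, no carryover and N=150, unqualified positives would fall to about 79%. The current rule (*either*) gives 83–85% with a period effect of 3 and about 95% with none. Judge agreement instead from the size and direction of the two estimates and their intervals.

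The cost is a few sentences and no new data. The downside should be stated openly: without washout, unequal carryover biases the primary estimate by half the carryover difference, with the rejection rates given under the objection. The sequence contrast is a weak safeguard. Its 95% half-width at N=150 is 11·√(2(1+ρ))·√(2/75)·1.976, or 5.1 to 6.1, and its power for a one-sided carryover of 5 is 36–49%. That is why the first-period result should always be shown.

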2.2 Aim and Hypotheses

We aim to compare the Nifty Feeding Cup to a standardized, generic cup in up to 200 caregivers and their preterm infants. We will test the hypotheses that Nifty Feeding Cup feeding compared to generic cup feeding will result in:

Primary:

1. Less spillage.
2. Greater caregiver satisfaction

Secondary:

3. Greater intake of milk (accounting for spillage, exploratory)
4. Shorter feeds (exploratory)
5. Greater caregiver satisfaction 4 weeks post-discharge

Our aim and hypotheses were selected based on the most informative outcomes given the scope of the funding. The above hypotheses are framed in terms of the statistical alternative which is typically more intuitive to non-statisticians.

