5.2.2 Outcomes

Outcomes related to intake, spillage, and duration will be measured at each Feeding Assessment, which will take place at Visit 2 through 5. Caregiver satisfaction will be measured during Feeding Assessment related to the experience of that feed (V2-V5). Caregiver satisfaction will be measured with the In-Hospital Preference Survey (V5) and the Follow-up Survey (V6).

Milk Intake. We will measure amount (in ml) and weight (in grams) of milk in the cup before the feeding. We will measure the amount and weight of milk in the cup after the feeding. If the cup is refilled, we will measure the amount and weight before and after the refill. The amount and weight will be recorded on the Feeding Assessment case report form. We will use a digital scale

to determine all weight measurements. The weight per ml will be estimated based on the baseline measure and used to adjust the gross measure of intake by subtracting out spillage that occurred during the feed. We will calculate intake per feed from these measures less the amount spilled.

Spillage. We will account for spillage of milk by using a baby bib cloth for all feedings. Each caregiver-infant pair will be provided with a bib cloth for each observed feeding. The bib cloth will be weighed before and after each feed and the weights recorded on the Feeding Assessment form. The difference between the pre and post weights will be used as the measure of the amount spilled. A digital scale will be used and milk weight will be in grams. Spillage will be reported as a percent with the amount of milk in grams spilled/mopped up divided by the total amount of milk weighed in grams less the total amount of milk not used.

Caregiver Satisfaction. Our primary measure of caregiver's satisfaction will be the cup she prefers [secondary] and rated satisfaction [primary] which will be recorded in the In-Hospital Preference Survey completed after the caregiver has finished the feeding portion of the study (V5). A secondary measure will be what the caregiver reports uses most of the time measured in the Follow-up Survey 4 weeks post-discharge (V6). We will also measure the caregiver's satisfaction with each cup after each feeding measured in the Feeding Assessment and in the In-Hospital Preference Survey (V2-V5).

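### Two primary hypotheses are each tested at an unsplit two-sided 0.05 with no stated multiplicity rule, which raises the chance of at least one false primary rejection to as much as 9.75% if the tests are independent

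*Combined protocol and SAP*

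**What the plan says.** Section 2.2 introduces its list with "We will test the hypotheses that Nifty Feeding Cup feeding compared to generic cup feeding will result in" and places two items under the primary label: "1. Less spillage" and "2. Greater caregiver satisfaction". Milk intake, feed duration and satisfaction four weeks after discharge follow as secondary, the first two marked exploratory.

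Section 3.1 contains the only significance rule: "Consistent with our power calculations, a two-sided p-value of 0.05 will be used". It names generalized estimating equations for intake, spillage and duration, and a sign test for cup preference.

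Section 2.3 says "Power for this study was determined by our primary hypotheses for the study", then identifies those hypotheses as "H_A 1 related to amount of spillage and H_A 2 related to intake of milk". It claims enough pairs to "detect at least a 5% difference in spillage or intake with 90% power and an alpha of 0.05 if no design effects are present", gives 80% if carryover is seen, and extends the calculation to satisfaction. Section 5.2.2 labels the satisfaction measures as "the cup she prefers [secondary] and rated satisfaction [primary", both taken from the survey at V5.

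Sections 1.0 to 19.0 contain no alpha split, testing order, adjustment, or rule that both primaries must be met.

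**The concern.** With two primary hypotheses and one unsplit threshold, the reader cannot tell what counts as a positive trial. Nothing prevents either result on its own from being reported as a positive primary finding. Used that way, the 0.05 describes each test but not the pair, and the chance that at least one primary is falsely rejected is higher.

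The family itself is also unsettled. Section 2.2 makes intake secondary and exploratory, whereas section 2.3 calls it the second primary hypothesis. Until both the family and the rule are fixed, the choice of which result to present as primary can be made after the data are seen. The trial is meant to supply the evidence base for wider use of the cup (section 2.1), so that choice should be closed in advance.

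**Working it through.** **Inputs from the plan.** Two primary hypotheses (2.2). Two-sided 0.05 per test (2.3, 3.1). 150 pairs, up to 200; SD 11, unit not stated; within-pair correlation 0.02 to 0.5; paired t-test (2.3).

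**Assumptions.** The 5% difference means 5 units on the scale where the SD is 11. The correlation between the two primary test statistics is not given, so 0, 0.5 and 0.9 are shown. It is a different quantity from the within-pair correlation.

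**Step 1: the plan's own power figures.** SD of the paired difference = 11 × √(2(1 − r)), which is 15.40 at r = 0.02 and 11.0 at r = 0.5.
- Crossover, 150 pairs, alpha 0.05, exact noncentral t: 97.7% (r = 0.02) to 99.98% (r = 0.5). The stated 90% is met but not reproduced; it would need only about 102 pairs at r = 0.02, or 53 at r = 0.5.
- First-cup-only comparison, 75 per order: standard error = 11 × √(2/75) = 1.796 and 5/1.796 = 2.78. Exact power is 79.0% at alpha 0.05 (79.5% by normal approximation), which matches the stated 80%. At alpha 0.025 it is 69.8%. The 80% therefore fits only the full 0.05, which supports reading each test as planned at unsplit alpha.

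**Step 2: error rate when neither outcome differs.**
- Either direction, independent tests: 1 − 0.95² = 0.0975.
- Favouring Nifty only, independent tests: 1 − 0.975² = 0.0494.
- Correlated test statistics: bivariate normal probability with cut-off 1.96.

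| Correlation of test statistics | At least one rejection, either direction | At least one rejection favouring Nifty | Either direction, smaller p against 0.025 |
|---|---|---|---|
| 0 | 9.75% | 4.9% | 4.94% |
| 0.5 | 9.1% | 4.5% | 4.65% |
| 0.9 | 7.0% | 3.5% | 3.6% |
| Single test | 5% | 2.5% | – |

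The last column is also the Holm rate here: when neither outcome differs, Holm makes a false rejection only if the smaller p-value passes 0.025.

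If intake were treated as a third primary, three independent tests would give 1 − 0.95³ = 14.3%.

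**Step 3: power for a test held at 0.025.**

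| Setting | Alpha 0.05 | Alpha 0.025 |
|---|---|---|
| Crossover, 150 pairs, r = 0.02 | 97.7% | 95.6% |
| Crossover, 150 pairs, r = 0.5 | 99.98% | 99.95% |
| Stated 90% taken at face value | 90% | about 84% |
| First cup only, 75 per order | 79% | 70% |
| First cup only, 100 per order | 89% | 83% |

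The third row uses the normal approximation: 1.960 + 1.282 − 2.241 = 1.00, and Φ(1.00) = 0.84.

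**The case against.** The strongest reply is that the plan promises no familywise rate. Sections 2.3 and 3.1 give a level per test, spillage and satisfaction are different constructs, and whether to adjust across separately stated questions is partly convention. That stands: a reader might infer that the plan breaks a stated 5% overall guarantee, and it does not. What remains is that no success rule is written. Requiring both primaries would remove the inflation, but no section says so.

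A reader might also take the 9.75% to mean that roughly one null trial in ten would falsely claim a benefit for Nifty. The documents do not support that. The figure counts rejections in both directions, while the hypotheses in 2.2 point one way. False claims favouring Nifty are about 4.9% at most, still about twice the 2.5% of a single test.

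It is tempting to add that satisfaction is rated by a caregiver who knows which cup she used, so a lone satisfaction result is the likelier false claim. That is an argument about bias. A multiplicity procedure does not correct bias, and the documents allow no figure to be put on it.

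Finally, a reader might conclude that adjustment costs at most two points of power. That depends on reading 5% as 5 units on the SD 11 scale. Section 2.3 gives the SD no unit and cites earlier differences in ml, and those inputs do not return the stated 90%.

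**Conclusion.** The concern holds as an unstated multiplicity rule for two primary hypotheses. Three conditions apply: either result alone can support a primary claim, neither outcome truly differs, and each is tested at two-sided 0.05. The chance of at least one false primary rejection is then 9.75% for independent tests and falls as their correlation rises, to 7.0% at 0.9. The part favouring Nifty runs from about 4.9% to 3.5%, against 2.5% for one test. The endpoint correlation is unknown, so the range should be quoted rather than a single value.

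The gap does not invalidate the trial, but it should be closed before analysis. The conflict between 2.2 and 2.3 over the second primary has to be settled first, because it decides which tests any rule covers.

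**What to change.** 1. Reconcile 2.3 with 2.2 so that both name the same two primary hypotheses. The wording in step 3 assumes that 2.2 stands and intake remains secondary and exploratory.
2. In 3.1, name the test for rated satisfaction at V5. The sign test there is for preference, which 5.2.2 tags as secondary. Holm cannot be run without this.
3. Replace the significance sentence in 3.1 with: *The two primary hypotheses (spillage percent; rated satisfaction at V5) will be tested by the Holm procedure at an overall two-sided 0.05: the smaller p-value against 0.025 and, if it passes, the larger against 0.05. Hypotheses 3 to 5 and all other tests will be reported without a confirmatory claim.*
4. Restate power in 2.3 at the new level, giving the unit of the SD and of the 5% difference.

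If the sponsor intends that both primaries must succeed, writing that rule down would equally resolve the point.

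**Cost.** The edits cover 2.3 and 3.1. The power losses in step 3 of the working are the worst case, for a test held at 0.025. Holm loses less, because once one primary passes, the other is tested at 0.05. The crossover cost is about 2 points or less on the 5-unit reading, but about 6 points if the stated 90% is taken at face value. The fallback loses about 9 points at 75 per order (79% to 70%) and about 6 at 100 per order (89% to 83%), so the stated 80% would have to be revised. By normal approximation, keeping 80% in the fallback at 0.025 would need about 93 per order instead of 76, or 186 pairs in total, within the 200 allowed.
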